### 3 INTRODUCTION

The purpose of this statistical analysis plan (SAP) is to describe the procedures and the statistical methods that will be used to analyze and report results for Eisai Protocol E7438-J081-206 (EZH-206).

#### 3.1 Study Objectives

##### 3.1.1 Primary Objective

The primary objective of the study is to assess the efficacy of tazemetostat in patients with relapsed or refractory B-cell non-Hodgkin's lymphoma (NHL) below by objective response rate (ORR).

Cohort 1: Follicular lymphoma (FL) with EZH2 gene mutation

Cohort 2: Diffuse large B-cell lymphoma (DLBCL) with EZH2 gene mutation

##### 3.1.2 Secondary Objectives

To assess the efficacy of tazemetostat by the endpoints below.

- Progression-free survival (PFS)
- Duration of response (DOR)
- Time to response (TTR)

To assess the safety of tazemetostat.

##### 3.1.3 Exploratory Objectives

- (1) To explore the pharmacokinetics (PK) of tazemetostat.
- (2) To explore the frequency of EZH2 gene mutation in B-cell NHL.

#### 3.2 Overall Study Design and Plan

This is a multicenter, open-label, phase 2 study in relapsed or refractory B-cell NHL patients with EZH2 gene mutation, consists with 2 cohorts. The study will assess efficacy and safety of tazemetostat in FL patients with EZH2 gene mutation in cohort 1, and DLBCL (including primary mediastinal B-cell lymphoma and transformed FL) patients with EZH2 gene mutation

in cohort 2.

## 4 DETERMINATION OF SAMPLE SIZE

In cohort 1, 8 efficacy evaluable FL patients with EZH2 mutation are required to detect lower limit of the 90% CI that exceed the 10% threshold in ORR, which is the primary endpoint of the study, with the expected ORR of 50% with power of approximately 80%.

In cohort 2, 13 efficacy evaluable DLBCL patients with EZH2 mutation are required to detect lower limit of the 90% CI that exceed the 10% threshold in ORR, which is the primary endpoint of the study, with the expected ORR of 40% with power of approximately 80%.

## 5 STATISTICAL METHODS

All descriptive statistics for continuous variables will be reported using mean, standard deviation (SD), median, minimum and maximum. Categorical variables will be summarized as number (percentage) of subjects.

### 5.1 Study Endpoints

#### 5.1.1 Primary Endpoint

- ORR of BOR

#### 5.1.2 Secondary Endpoints

- PFS
- DOR
- TTR
- Safety assessments (AEs, clinical laboratory tests, vital signs, body weight, 12-lead ECGs, ECOG-PS, and physical examinations)

#### 5.1.3 Exploratory Endpoints

- Concentration of tazemetostat
- Frequency of EZH2 gene mutation

## 5.2 Study Subjects

### 5.2.1 Definitions of Analysis Sets

**Efficacy Analysis Set** will include efficacy evaluable subjects who received at least 1 administration of the study drug and who has appropriate tumor assessment data of Screening 2 and post-baseline.

**Pharmacokinetic Analysis Set** will include subjects who received at least 1 administration of the study drug and had at least 1 concentration data of tazemetostat.

**Biomarker Analysis Set** will include subjects who have conducted EZH2 gene mutation assessment at Screening 1.

**Safety Analysis Set** will include subjects who received at least 1 administration of the study drug.

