9.5.1.3 Efficacy Assessments

Efficacy assessment will be performed by investigator or subinvestigator based on "Revised response criteria for malignant lymphoma (IWG-2007)" (Cheson, et al., 2007). Overall response and best overall response (BOR) (best response recorded at the designated visits during the study) will be assessed. Perform the assessment below for tumor assessment.

CT scans will be performed at Screening 2, every 8 weeks from study drug administration up to first 32 weeks, then every 12 weeks and at discontinuation.

Eisai Confidential Page 42 of 71 FINAL: 29 Jan 2021

PET scans will be performed at Screening 2. If positive, perform when it is required to confirm CR as soon as possible or when clinically indicated.

If gastrointestinal disease is suspected, endoscopic examination will be performed at Screening 2. If exists, perform when it is required to confirm CR as soon as possible or when clinically indicated.

To evaluate bone marrow infiltration, a bone marrow aspiration or biopsy will be performed at Screening 2. If positive or indeterminate, perform when it is required to confirm CR as soon as possible or when clinically indicated.

Also, central review will be conducted by the Imaging Review Committee for CT and PET assessment. In addition, Efficacy and Safety Evaluation Committee (ESEC) will conduct central evaluation based on the review of Imaging Review Committee and other assessment / bone marrow infiltration evaluated by the investigator or subinvestigator, to determine the overall responses and the best overall response.

The primary endpoint and the secondary endpoint with regard to efficacy are defined as below, and will be evaluated by the result of ESEC review.

ORR:

The rate of subjects whose BOR is CR or PR.

PFS

Defined as the term between the date of administration of the first dose of the study drug and the date of the first event (PD or death whichever occurs first). The detail of the censoring rule for PFS will be described in the statistical analysis plan (SAP).

• DOR:

Defined as the term between the date of confirmation of the first response and the date of confirmation of the PD. The detail of the censoring rule for DOR will be described in the SAP.

TTR·

Defined as the term between the date of administration of the first dose of the study drug and the date of confirmation of the first response.

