- c: Obtain from the patients who has confirmed tumor EZH2 gene mutation in central laboratory.
- d: Collect demography information described in Section 9.5.1.1.
- e: Blood samples for PK analyses of tazemetostat will be collected in C1D15 and C2D1 predose of first administration.
- f: The data of CT scan/endoscopy before informed consent within 28 days from study drug administration can be used as Screening 2 data if it meets the requirement of the protocol. Perform tumor assessment at Screening 2, every 8 weeks from first study drug administration for first 32 weeks (±1 week, eg, C2D21 to C3D7, C4D21 to C5D7...C8D21 to C9D7), then every 12 weeks (±1 week, eg, C11D21 to C12D7, C14D21 to C15D7...) and discontinuation. The data within 28 days can be used as discontinuation data. If gastrointestinal disease were suspected, endoscopic examination will be performed at Screening 2. If exists, perform when it is required to confirm CR as soon as possible or when clinically indicated.
- g: The data of PET scan before informed consent within 28 days from study drug administration can be used as Screening 2 data if it meets the requirement of the protocol. If positive, perform when it is required to confirm CR as soon as possible or when clinically indicated.
- h: The data of bone marrow examination before informed consent within 42 days from study drug administration can be used as Screening 2 data if it meets the requirement of the protocol. If positive or indeterminate, perform when it is required to confirm CR as soon as possible or when clinically indicated.
- i: Subjects should not take study drug before evaluations are performed, unless specified (except tumor assessments and peripheral blood smear morphology assessment).
- j: On Day 15 of each cycle, peripheral blood smear morphology assessment can be omitted at the discretion of the investigator or subinvestigator, if there was no concern for safety of the subject.
- k: In Cycle 13 or later, visits and assessments on Day 15 can be omitted at the discretion of the investigator or subinvestigator, if there was no concern for safety of the subject.
- 1: Final observation is unnecessary for subjects who meet approved indication and receive commercial tazemetostat.

Eisai Confidential Page 53 of 71

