9.7.1.2 Definitions of Analysis Sets

Efficacy Analysis Set will include efficacy evaluable subjects who received at least 1 administration of the study drug and who has at least 1 appropriate tumor assessment data of Screening 2 and post-baseline.

Eisai Confidential Page 58 of 71

Pharmacokinetic Analysis Set will include subjects who received at least 1 administration of the study drug and had at least 1 concentration data of tazemetostat.

Biomarker Analysis Set will include subjects who have conducted EZH2 gene mutation assessment at Screening.

Safety Analysis Set will include subjects who received at least 1 administration of the study drug.

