### 5.3 Data Analysis General Considerations

All efficacy analyses will be conducted based on the Efficacy Analysis Set.

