### 5.3.5 Handling of Missing Data, Dropouts, and Outliers

No imputation will be performed for missing data.

Data exceptions will be identified before data base lock based on discussion with medical experts if necessary.

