### 5.4.2 Secondary Efficacy Analyses

- Analysis of PFS

PFS will be summarized by Kaplan-Meier method using median with 95%CI. Kaplan-Meier curve will be provided. The number of event/censor (percentage) and reasons of censor will be also summarized.

- Analysis of DOR

DOR will be summarized by Kaplan-Meier method using median with 95% CI in responders. The number of event/censor (percentage) and reasons of censor will be also summarized.

- Analysis of TTR

TTR will be summarized using descriptive statistics in responders.

PFS will be calculated as:

End date for PFS – Date of administration of the first dose of study drug + 1 (day)

DOOR will be calculated as:

End date for DOOR – Date of the first response + 1 (day)

End date of PFS and DOOR is defined as the table below:

Situation	End Date for PFS and DOOR	Censored
Documented progression disease (PD) during the study	Date of the first assessment of the series of the tests that determined PD	No
Death during the study before PD	Date of death	No
No baseline assessments	Date of administration of the first dose of study drug	Yes
Treatment discontinuation without post-baseline tumor assessments	Date of administration of the first dose of study drug	Yes
Treatment discontinuation without documented PD or death with post-baseline tumor assessments	Date of last tumor assessment before discontinuation	Yes
New anticancer treatment started prior to disease progression	Date of last tumor assessment before start of new treatment	Yes
Death or PD after more than one missed tumor assessments	Date of the last tumor assessment before missed assessments	Yes
Subjects still on treatment without PD as of data cut-off	Date of last tumor assessment	Yes

TTR will be calculated as:

Date of first response – Date of administration of the first dose of study drug + 1 (day)

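### The only efficacy analysis set drops treated subjects who have no post-baseline scan, which can only raise ORR and removes deaths before the first scan from PFS; no all-treated analysis is planned

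*SAP*

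**What the plan says.** Protocol 9.7.1.2 admits to the Efficacy Analysis Set a dosed subject "who has at least 1 appropriate tumor assessment data of Screening 2 and post-baseline". SAP 5.2.1 keeps the restriction in nearly the same words: "who received at least 1 administration of the study drug and who has appropriate tumor assessment data of Screening 2 and post-baseline". Neither document defines an appropriate assessment.

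SAP 5.3 states: "All efficacy analyses will be conducted based on the Efficacy Analysis Set". SAP 5.3.5 adds: "No imputation will be performed for missing data". SAP 5.4.3 lists no other efficacy analyses, and the changes listed in SAP 7 are 95% CIs and subgroups. The Safety Analysis Set contains every dosed subject, but SAP 5.6 assigns it to safety.

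CT is scheduled at Screening 2 and then "every 8 weeks from study drug administration up to first 32 weeks, then every 12 weeks and at discontinuation" (Protocol 9.5.1.3), so the first scheduled on-treatment scan is at Week 8. For the discontinuation scan, footnote f of Protocol Table 5 says: "The data within 28 days can be used as discontinuation data". It does not say that the scan must come after the first dose.

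Protocol 9.5.1.3 ends PFS at the earlier of progression and death. The end-date table in SAP 5.4.2 makes death before progression an uncensored event. It also has a row, "Treatment discontinuation without post-baseline tumor assessments", that censors at the first dose.

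**The concern.** Entry to the primary analysis set depends on something that happens after treatment starts. Subjects who die, refuse or are lost before any scan are unlikely to be a random sample of those treated, and none of them can have a best response of CR or PR. Leaving them out shrinks the denominator and leaves the numerator unchanged.

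For PFS, the set definition and the end-date table do not fit together. A death before the first scan is an event under the table, but the subject is not in the set. The row for discontinuation without a post-baseline assessment has nobody to apply to. The one way it could is if an assessment judged appropriate by the investigator is judged inappropriate by the committee, or the reverse, and neither document raises this. Early deaths are the PFS events most likely to be lost.

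With 8 and 13 subjects, one or two exclusions can decide whether the lower limit clears 10%. The planned tables contain no ORR or interval that would show it.

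**Working it through.** **Inputs from the documents.** SAP 4 gives 8 evaluable FL subjects (expected ORR 50%) and 13 evaluable DLBCL subjects (expected ORR 40%). The lower limit of the 90% CI is to exceed 10%, with power of about 80%. SAP 5.4.1 specifies a two-sided exact Clopper–Pearson interval. Protocol 9.3 states the enrolment targets in evaluable subjects.

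**Assumption.** The documents give no unevaluable rate, so *u* is varied over 0, 5, 10 and 20%. Unevaluable subjects count as non-responders.

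**1. The plan's own figures.** The lower limit for *x* responders in *N* is the 5th percentile of Beta(*x*, *N*−*x*+1).

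- FL: 2/8 gives 4.6% and 3/8 gives 11.1%, so at least 3 responses are needed. P(X≥3 | 8, 0.50) = 85.5%. With *n* = 7 it is 77.3%.
- DLBCL: 3/13 gives 6.6% and 4/13 gives 11.3%, so at least 4 are needed. P(X≥4 | 13, 0.40) = 83.1%. With *n* = 12 it is 77.5%.

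Both sample sizes reproduce as the smallest that reach 80%.

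**2. Direction.** With *k* treated but unscanned subjects, the evaluable ORR is *x*/*N* and the all-treated ORR is *x*/(*N*+*k*). The first is never smaller. They are equal only if *k* = 0 or *x* = 0.

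**3. Sensitivity at the minimum passing count.**

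| Cohort | Excluded | Result | 90% lower limit | Above 10%? |
|---|---|---|---|---|
| FL | 0 | 3/8 | 11.1% | yes |
| FL | 1 | 3/9 | 9.8% | no |
| DLBCL | 0 | 4/13 | 11.3% | yes |
| DLBCL | 1 | 4/14 | 10.4% | yes |
| DLBCL | 2 | 4/15 | 9.7% | no |

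**4. Chance of meeting the criterion when the all-treated ORR is 10%.** The ORR among evaluable subjects is then 0.10/(1−*u*). The evaluable-set figure is P(X≥3 | 8, 0.10/(1−*u*)) for FL and P(X≥4 | 13, 0.10/(1−*u*)) for DLBCL. For the all-treated criterion, enrolment runs until 8 or 13 are evaluable, so the number unevaluable, *m*, is negative binomial. The exact limit is taken at *N* = *n* + *m*.

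| *u* | Evaluable set, FL / DLBCL | All treated, FL / DLBCL |
|---|---|---|
| 0 | 3.8% / 3.4% | 3.8% / 3.4% |
| 5% | 4.4% / 4.0% | 3.1% / 3.5% |
| 10% | 5.0% / 4.8% | 2.6% / 3.2% |
| 20% | 6.7% / 6.9% | 2.1% / 2.6% |

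The evaluable-set figure passes the nominal one-sided 5% at *u* of about 10.0% (FL) and 11.2% (DLBCL).

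**5. Power if the all-treated criterion were made primary.** This uses the same enrolment scheme. The answer depends on which ORR is held at 50%/40%.

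| *u* | 50%/40% is the evaluable ORR | 50%/40% is the all-treated ORR |
|---|---|---|
| 5% | 78% / 80% | 82% / 84% |
| 10% | 73% / 75% | 82% / 84% |
| 20% | 67% / 68% | 88% / 88% |

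SAP 4 states its assumptions for evaluable subjects, so the left column follows the plan's wording.

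**The case against.** The evaluable set is openly pre-specified and the sample size was planned on it. If the 10% threshold is read on the evaluable scale, the chance of wrongly meeting it is 3.8%/3.4% at every *u*. The rise in step 4 appears only when the null is set for all treated subjects. That is correct, and it is why the scale is labelled. The all-treated scale still answers the question a reader of the trial will ask.

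The effect may be small or nil. Eligibility requires ECOG 0–1 and a life expectancy of at least 3 months, and a CT is due at discontinuation, so an early stopper who is scanned stays in as a non-responder. A reversal needs both a borderline count and exclusions. At the expected ORRs and *u* = 5%, the chance is 0.219 × (1 − 0.95⁸) = 7.4% for FL (exactly 3 responses, at least one excluded). For DLBCL it is 0.184 × 0.153 = 2.8% (exactly 4 responses, at least two excluded). This stands and limits the importance of the point.

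The upward direction belongs to the post-baseline condition. The Screening 2 condition, with an appropriate assessment left undefined, could in principle remove a responder. This also stands.

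The 10% threshold appears only in the sample-size rationale, and SAP 5.3.3 plans no statistical comparison. Passing here therefore means meeting the design criterion, not a formal test.

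Finally, disposition counts (SAP 5.2.2), baseline tables for the safety and efficacy sets (SAP 5.2.3) and the swimmer plot (SAP 5.6.1) would let a careful reader rebuild an all-treated ORR. They would not supply a pre-specified estimate or interval, and they do not restore early deaths to PFS.

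**Conclusion.** The concern holds and should be fixed. Every efficacy analysis is conditional on a post-baseline scan, no all-treated ORR or PFS is planned, and the PFS end-date table contradicts the set definition.

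The upward effect on ORR is relative to counting unscanned subjects as non-responders, and it is zero if all treated subjects are scanned. At the minimum passing count, one exclusion (FL) or two (DLBCL) take the lower limit below 10%. Inflation of the false-pass chance beyond 5% needs an unevaluable rate above roughly 10–11%, a rate the documents neither give nor rule out. The contradiction over PFS does not depend on any assumed rate. DOR and TTR are restricted to responders and are unaffected.

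**What to change.** In SAP 5.2.1, 5.3 and 5.4:

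- Pre-specify for each cohort an ORR with its exact 90% CI on all treated subjects (the existing Safety Analysis Set). Count unassessed subjects as non-responders and report the result beside the evaluable-set ORR. The evaluable set can remain primary, because the sample size was planned on it.
- Analyse PFS on all treated subjects. State that a death before the first scan is an event at the date of death and takes precedence over the row that censors at first dose.
- Define an appropriate assessment, and say whether set membership can differ between the committee and investigator reads.

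The cost is SAP wording and one table from data already collected. The all-treated ORR will be equal to or lower than the evaluable one. As a supporting analysis it leaves the planned power unchanged. If the sponsor made it primary, power at the plan's evaluable ORRs would fall from 85.5%/83.1% (FL/DLBCL) to the levels in the left column of step 5, and that should be disclosed.

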### 5.2.2 Subject Disposition

The number of subjects who signed informed consent (for tumor EZH2 gene mutation test and study treatment), were registered in the study, and failed screening (Screening 1 and Screening 2) and the primary reason for screen failures will be summarized for each disease (cohort). The number and percentage of subjects who were treated, were not treated, were ongoing, and discontinued from study and the primary reason for discontinuation will be summarized for each disease (cohort).

### 5.2.3 Demographic and Other Baseline Characteristics

Demographic and other baseline characteristics for the Safety/Efficacy Analysis Set will be summarized for each disease (cohort) and overall. Continuous demographic and baseline variables include age, body weight, height and Median time from initial diagnosis; categorical variables include age group(<65, 65<=), sex, race, ethnicity, ECOG-PS, Ann Arbor Staging at Screening, previous therapies (radiotherapy, chemotherapy, autologous stem cell transplantation and other medication for lymphoma), B symptoms, disease diagnosis (including COO) and Baseline Bone Marrow assessment.

## MEDICAL HISTORY AND CURRENT MEDICAL CONDITION

A subject data listing of medical history and current medical conditions will be provided.

### 5.2.4 Prior and Concomitant Therapy

For the Efficacy Analysis Set, the number and percentage of subjects with each previous therapies (radiotherapy, systemic chemotherapy, autologous stem-cell transplantation, other medication for lymphoma) will be provided for each disease (cohort) and overall. The

number and percentage of subject with each previous systemic chemotherapy will also be provided for each disease (cohort) and overall.

All investigator terms for medications recorded in the CRF will be coded to an 11-digit code using the World Health Organization Drug Dictionary (WHO DD) preferred name. Prior medications will be defined as medications that stopped before the first dose of study drug. Concomitant medications will be defined as medications that started before the first dose of study drug and were continuing at the time of the first dose of study drug, or started on or after the date of the first dose of study drug up to the final observation. All prior and concomitant medications will be presented in subject data listings.

#### 5.2.5 Treatment Compliance

Not calculated.

### 5.3 Data Analysis General Considerations

All efficacy analyses will be conducted based on the Efficacy Analysis Set.

#### 5.3.1 Pooling of Centers

Subjects from all centers will be pooled for all analyses.

#### 5.3.2 Adjustments for Covariates

No adjustment for covariates will be performed.

#### 5.3.3 Multiple Comparisons/Multiplicity

No statistical comparison is planned in this study.

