9.7.1.6 Efficacy Analyses

FINAL: 29 Jan 2021

This analysis will be performed on the Efficacy Analysis Set. All summary of efficacy will be conducted for each disease (cohort).

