9.7.2 Determination of Sample Size

In cohort 1, 8 efficacy evaluable FL patients with EZH2 mutation are required to detect lower limit of the 90% CI that exceed the 10% threshold in ORR, which is the primary endpoint of the study, with the expected ORR of 50% with power of approximately 80%.

In cohort 2, 13 efficacy evaluable DLBCL patients with EZH2 mutation are required to detect lower limit of the 90% CI that exceed the 10% threshold in ORR, which is the primary endpoint of the study, with the expected ORR of 40% with power of approximately 80%.

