## 5.4 Efficacy Analyses

All efficacy result will be summarized by disease (cohort) and overall. Results from central assessment by Efficacy and Safety Evaluation Committee and investigator assessment will be used.

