### 5.4.1 Primary Efficacy Analyses

BOR will be summarized. The rate of subjects whose BOR is CR or PR is calculated as ORR, and its corresponding 2-sided exact 90% confidence intervals (CIs) using the method of Clopper–Pearson will also be calculated. A waterfall plot will be presented for the percent changes from baseline in the sum of the product of diameters of target lesions at post-baseline nadir. Also, percent change from baseline over time will be presented using spider plot. Regarding the ORR, 95% CIs will also be calculated.

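### Does the SAP lose the protocol's rule that the 90% CI lower limit must exceed 10%, by planning no comparison and adding a 95% CI and a pooled response rate?

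*SAP*

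**What the plan says.** - **The rule.** Protocol 9.7.2 gives it by cohort: "8 efficacy evaluable FL patients with EZH2 mutation are required to detect lower limit of the 90% CI" for FL and "13 efficacy evaluable DLBCL patients with EZH2 mutation are required to detect lower limit of the 90% CI" for DLBCL, each against a 10% threshold, with expected ORRs of 50% and 40% and power of about 80%. SAP Section 4 repeats it; in both cohorts the planned number is "required to detect lower limit of the 90% CI that exceed the 10% threshold in ORR".
- **The primary analysis.** Protocol 9.7.1.6.1 and SAP 5.4.1 both ask for the ORR with a two-sided exact (Clopper–Pearson) 90% CI. Neither section repeats the 10% threshold. SAP 5.4.1 then adds: "Regarding the ORR, 95% CIs will also be calculated". SAP Section 7 declares this addition.
- **Comparisons.** SAP 5.3.3 states: "No statistical comparison is planned in this study".
- **Who assesses.** Protocol 9.5.1.3 says the primary endpoint and the secondary efficacy endpoints "will be evaluated by the result of ESEC review". SAP 5.4 uses both the ESEC and the investigator results, naming ESEC first. SAP 5.3.4 and Section 7 describe the ORR analysis as based on independent review.
- **Pooling.** Protocol 9.7.1.6 says "All summary of efficacy will be conducted for each disease (cohort"). SAP 5.4 says "All efficacy result will be summarized by disease (cohort) and overall". Section 7 does not list this difference.

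**The concern.** A lower confidence limit set against 10% is a test against a fixed value, and the study does it twice. A SAP that plans no comparison seems to withdraw that test. Placing a 95% CI beside the 90% CI without saying which one decides could then allow a choice after the data are seen, and in samples this small the choice can matter. Investigator results in an open-label study raise a similar worry.

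The overall summary is a separate issue. A pooled ORR depends on the 8:13 mix of two diseases and answers no stated question. It could look favourable on FL responses alone. The protocol allows whole-study summaries for baseline and safety data but words efficacy by cohort only, so the SAP appears to have widened the scope without recording it.

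At stake would be whether a borderline cohort is called positive, and whether a weak DLBCL result could be hidden.

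**Working it through.** **Inputs.** n = 8 and 13, threshold 10%, expected ORRs 50% and 40%, power about 80% (protocol 9.7.2, SAP Section 4); exact CIs (protocol 9.7.1.6.1, SAP 5.4.1); interim response rates 12/13 and 5/17 (protocol 7.4.1.4).

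**Formula.** The Clopper–Pearson lower limit for x of n at level c is the (1 − c)/2 quantile of a Beta(x, n − x + 1) distribution. It exceeds 10% exactly when P(X ≥ x | n, 0.10) < (1 − c)/2, which is 5% for the 90% CI and 2.5% for the 95% CI.

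**Step 1: reproduce the design.**
- FL, x = 3: P(X ≥ 3 | 8, 0.10) = 1 − (0.43047 + 0.38264 + 0.14880) = 3.81%, below 5%. Power at 50% = 1 − (1 + 8 + 28)/256 = 85.5%. With n = 7 (3 responders needed) power is 77.3%.
- DLBCL, x = 4: P(X ≥ 4 | 13, 0.10) = 1 − (0.25419 + 0.36716 + 0.24477 + 0.09972) = 3.42%, below 5%. Power at 40% = 1 − (0.00131 + 0.01132 + 0.04528 + 0.11068) = 83.1%. With n = 12 (4 responders needed) power is 77.5%.

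So 8 and 13 are the smallest sizes that reach 80% power under the 90% CI rule.

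**Step 2: compare the two intervals.** Both tail probabilities lie between 2.5% and 5%, which is why the intervals disagree at these counts.

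| Result | 90% lower limit | 95% lower limit |
|---|---|---|
| FL 2/8 | 4.6% | 3.2% |
| FL 3/8 | 11.1% | 8.5% |
| FL 4/8 | 19.3% | 15.7% |
| DLBCL 3/13 | 6.6% | 5.0% |
| DLBCL 4/13 | 11.3% | 9.1% |
| DLBCL 5/13 | 16.6% | 13.9% |

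They disagree about 10% at 3/8 and 4/13 and nowhere else. At the expected ORRs these counts occur with probability 56/256 = 21.9% and 18.4%. At least one cohort lands there with probability 1 − (0.781 × 0.816) = 36%, taking the cohorts as independent.

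If the 95% CI decided, 4/8 and 5/13 would be needed. Power would be 163/256 = 63.7% for FL and 83.1% − 18.4% = 64.7% for DLBCL. The planned sizes therefore cannot have come from the 95% CI.

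The disagreement also depends on n: with 9 to 11 evaluable FL subjects both levels need 4 responders, and with 15 to 17 DLBCL subjects both need 5.

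**Step 3: the pooled rate.** With n = 21, six responders give a 90% lower limit of 13.2%, and five give 9.9%. So 6/8 in FL with 0/13 in DLBCL would clear 10% when pooled. The chance that the pooled rate clears 10% while DLBCL has 3 or fewer responders is:
- at the interim rates (12/13 and 5/17), 43.87%; the chance that DLBCL has 3 or fewer, ignoring pooling, is already 43.91%;
- at the planned rates (50% and 40%), 12.8%; the corresponding DLBCL figure is 100% − 83.1% = 16.9%.

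The large figure thus reflects DLBCL missing its own criterion if its true rate is 29%, and pooling does not cause that.

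**Step 4: read the sections together.** The 10% threshold is attached to the 90% CI in the protocol and again in the SAP. Nothing attaches it to the 95% CI or to the pooled rate. SAP 5.3.3 stands under the multiplicity heading of an uncontrolled study, where its natural meaning is that no groups are compared and no adjustment is made. Without adjustment, the chance that at least one cohort passes when both true rates are 10% is 1 − (0.96191 × 0.96584) = 7.1%. That is acceptable for two diseases judged separately.

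**The case for a change.** The strongest case is that the threshold appears only in sample-size text. No analysis section states a success criterion, and the SAP adds a second interval level, a second assessor and a pooled figure without ranking them. Reading SAP 5.3.3 as meaning no between-group test still leaves the threshold decision unstated. In an open-label study a stated hierarchy is good practice, and it would cost only a few sentences. On pooling, if FL responds at 50% and DLBCL at only 10%, the pooled lower limit would exceed 10% in 44.4% of trials.

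Part of this stands. A sentence of hierarchy would be tidier, and the overall efficacy summary does depart from protocol 9.7.1.6 without being listed in SAP Section 7. But the missing criterion goes back to protocol 9.7.1.6.1, so the SAP did not remove anything. The 95% CI is introduced as an addition and declared as one. The assessor is settled by the protocol, with which the SAP's references to independent review agree. The protocol does not forbid a pooled figure; that is inferred from its contrasting wording. An extra overall column also cannot hide DLBCL, whose own ORR and interval are required in the same summary.

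**Conclusion.** The concern does not call for a change. The arithmetic is right: the 90% and 95% limits straddle 10% at 3/8 and 4/13, and deciding on the 95% CI would cost about 22 points of power in FL (85.5% to 63.7%) and 18 in DLBCL (83.1% to 64.7%). That loss belongs to a rule neither document adopts. An analyst following both documents would report the ESEC-assessed ORR with its exact 90% CI in each cohort and set the lower limit against 10%, as the design intends.

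What remains is missing detail on hierarchy, which the sample-size and assessment sections supply, and a clerical omission of the overall efficacy summary from SAP Section 7. Correcting either would alter no primary estimate, interval or conclusion.

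This rests on three assumptions: the evaluable numbers are 8 and 13 (the counts, though not the CI rule, change otherwise); the SAP's independent review means the central ESEC assessment; and the pooled figure is reported only as description.
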